9.2 Patient Accrual and Expected Duration of the Trial

It is estimated that approximately 50-60% of the 450,000 survivors of childhood cancer who are alive in the U.S. today have received anthracyclines. Many pediatric cancer patients (approximately 20-25%) are being treated with anthracyclines with cumulative dose ≥ 250 mg/m², such as those with bone cancer and AML. Although exact estimates are not available, using the conservative estimates of 50% and 20% to calculate, $>30,000$ survivors would meet the current eligibility criteria. We expect thousands of childhood cancer survivors meeting such criteria are currently being followed at member COG institutions.

ACTIVATION PROTOCOL:

To answer the scientific questions, 250 randomized subjects (125 per arm) is required. Through a different mechanism, 82 patients have already been accrued and randomized. Therefore, this COG protocol aims to enroll and randomize an additional of 168 patients through this protocol, with a maximum accrual of 177 patients to account for up to 5% of ineligible enrollments. Given the large pool of potential eligible patients, we expect to complete the accrual, including the time it takes to open the study at COG institutions, over 4 years.

WITH AMENDMENT #4:

To answer the scientific questions, 182 subjects (91 per arm) who are randomized and start study drug are required. Through a different mechanism, 87 patients have already been accrued and randomized. Therefore, this COG protocol aims to enroll, randomize and start

treatment for an additional **95** patients through this protocol. To account for attrition, enrollment through this COG trial may proceed up to 109 patients. Given the large pool of potential eligible patients, we expect to complete the accrual, including the time it takes to open the study at COG institutions, over 5 years.

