The estimates from linear mixed effects model are valid in the presence of incomplete response data if missing data occurs at random. However, nonparticipation and dropouts may occur differentially between treatment groups for various reasons, possibly resulting in non-ignorable missing data. In addition to collecting information on reasons for nonparticipation, we will apply two analytic approaches to examine the effects of missing data on study results:¹²⁵ 1) pattern mixture models and 2) selection models. In pattern mixture models, the 16 possible missing data patterns (arising from 4 follow-up time points, with no missing data at t₀, and considering a response as missing if data from echocardiographic assessment are missing) will be used as covariates in the above-described bivariate linear mixed effects model. The effects of missing data on the estimate of treatment effect can be assessed. An overall estimate of the treatment effect may be obtained by averaging the estimates over the missing pattern groups. In the selection model, we will model the probability of dropout using baseline covariates to estimate the propensity for dropout. The propensity scores will be used as a covariate in the bivariate linear mixed effects model to adjust for the effects of dropout on treatment effects.

Secondary echocardiographic efficacy measures (afterload, systolic and diastolic measurements) will be evaluated by applying the same methods for longitudinal analysis. Significance of the carvedilol effects will be evaluated in the manner described above based on testing the significance of the interaction of time by group indicator variables. The distribution of continuous variables will be examined graphically and appropriate transformations made before applying analytical methods based on normal assumption.

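### As written, neither missing-data check in Section 9.3.1 examines the non-ignorable dropout it is meant to address

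*Combined protocol and SAP*

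**What the plan says.** Section 9.3.1 states that the mixed-model estimates hold if data are missing at random. It then warns that dropout may differ between arms, "possibly resulting in non-ignorable missing data", and offers two analyses to examine this.

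- **Pattern mixture model.** "the 16 possible missing data patterns", "arising from 4 follow-up time points" with baseline always present, "will be used as covariates in the above-described bivariate linear mixed effects model". The section adds: "An overall estimate of the treatment effect may be obtained by averaging the estimates over the missing pattern groups".
- **Selection model.** "we will model the probability of dropout using baseline covariates to estimate the propensity for dropout". Then: "The propensity scores will be used as a covariate in the bivariate linear mixed effects model".

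The section gives no rule for collapsing sparse patterns, no pattern-by-time or pattern-by-time-by-arm term, no averaging weights, no treatment of the pattern with baseline only, and no delta-adjusted or reference-based analysis. It also calls the model bivariate, although the model set out above it has one outcome, the LV T-D z-score.

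The text is current. Section 9.0 says Amendment #4 left the analysis plan unchanged, while the requirement became "182 subjects (91 per arm) who are randomized and start study drug are required" (Section 9.2; previously 125 per arm) and assumed attrition rose from 15% to 19% per year (Section 9.4).

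**The concern.** Dropout here is expected to be heavy and could be related to arm or outcome. Section 9.4 expects 56 of 91 patients per arm to remain. Section 8.1 removes patients from therapy for failed dose escalation, low adherence and adverse events, among other reasons, and then requires no further study evaluations except after a cardiac event or pregnancy. Patients removed at the Day 14 escalation leave before the first follow-up echocardiogram at Day 180.

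A sensitivity analysis for non-ignorable dropout is useful only if its answer can move when dropout depends on what was not observed. If both checks reproduce the primary slope difference by construction, their agreement will be reported as robustness when it carries little information about the problem Section 9.3.1 raises.

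**Working it through.** **1. The plan's own figures.** Four follow-up visits, each observed or missing, give 2^4 = 16 patterns, as stated. Linear loss of 19% per year gives 91 × (1 − 0.38) = 56.4 per arm (Section 9.4 states 56) and 182 × 0.62 = 112.8 in total (Section 9.5.2 states 114). Compound loss, 91 × 0.81² = 59.7, does not reproduce the 56.

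**2. Expected pattern sizes.** Loss per half-year is 91 × 0.095 = 8.6 per arm. Each arm therefore has about 56 completers and about 8.6 patients in each of four monotone dropout patterns (56.4 + 4 × 8.645 = 91). The other 16 − 5 = 11 patterns arise only through intermittent missed visits. The documents give no rate for these, so a range is assumed (20,000 multinomial draws of two arms of 91):

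| Assumed intermittent missingness per visit | 0% | 2% | 5% | 10% |
|---|---|---|---|---|
| Patterns lacking a patient in at least one arm (of 16) | 11.0 | 9.6 | 8.0 | 6.4 |
| Pattern-by-arm cells with fewer than 5 patients (of 32) | 22.5 | 22.4 | 21.8 | 20.0 |
| Baseline-only patients expected per arm | 8.6 | 8.8 | 9.1 | 9.6 |
| Patterns with an estimable treatment slope (16 − first row − 1) | 4.0 | 5.4 | 7.0 | 8.6 |

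The final −1 is the baseline-only pattern, which has patients but no slope. In no draw were all 16 patterns filled in both arms. At 5% intermittent missingness, about 12 to 15% of patients sit in patterns with no treatment-slope estimate.

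**3. Patterns as covariates.** Read literally, the model is: mean z = level for the pattern + b·time + g·arm + d·time·arm. The coefficient d is common to all patterns, and the patterns move only the level. The primary test is on d, which is estimated largely from within-patient change, where a term constant over time cancels.

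**4. Baseline propensity.** The score is a function of baseline covariates and is also constant over time within a patient. It contains no post-baseline z-score, observed or unobserved. If baseline covariates did explain dropout, missingness would be ignorable given them, which is not the case being checked.

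**5. Simulation.** All runs have no true treatment effect, so any 24-month difference is false. Mechanism A used 300 trials, 91 per arm, about 37% dropout, 5% intermittent missingness, individual slope SD 0.5 and correlation 0.7. B used 300 trials with a different mechanism and about 40% missing at 24 months. C is a third assumed mechanism.

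| Non-ignorable mechanism (assumed) | Plain mixed model | With pattern covariates | With baseline propensity |
|---|---|---|---|
| A | 0.152 | 0.152 | 0.152 |
| B | 0.180 | 0.180 | 0.179 |
| C | 0.216 | 0.216 | 0.217 |

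Under A the empirical SE was 0.141, so the simulation error of the mean is 0.141/√300 = 0.008. Against the projected effect of 0.4 (Section 9.4), the false differences are 0.152/0.4 = 38% to 0.216/0.4 = 54%. Once empty patterns were dropped, the pattern-covariate model could be fitted in every trial under A.

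**6. A collapsed pattern-mixture model.** Two groups (completers, dropouts) with group-by-time-by-arm terms, averaged with each arm's observed proportions, cut the false difference under A from 0.152 to 0.013. The SE rose from 0.141 to 0.194, so the detectable difference (1.96 + 0.84 = 2.80 times the SE) rose from about 0.40 to about 0.54, above the projected 0.4. When dropout depended only on observed post-baseline values, this model was itself biased, by −0.21.

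**The case against.** The strongest reply is that Section 9.3.1 is under-specified rather than wrong. It counts the possible patterns and says that an overall estimate may be obtained by averaging. It neither commits to 16 separate slopes nor bars collapsing. The two faults also belong to different readings: sparsity matters only if pattern-specific slopes are averaged, and the unmoved slope only if patterns are main effects. Truly empty patterns would take zero weight under observed-proportion weighting. All of this stands. It is why the two readings are kept apart here, and why the lasting gap under averaging is the baseline-only pattern together with patterns filled in one arm only.

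It is also fair that these are sensitivity analyses. The efficacy criterion is the 1-df slope test and its direction. Under Amendment #4, Appendix II asks only for support from the unstructured mean model before stopping. No current decision rule rests on these two checks. In addition, Section 8.1 exempts cardiac events from its waiver of further evaluations, so the most plainly outcome-related removals need not go unobserved, although the section does not say which assessments continue.

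None of this rescues the propensity model. Its inputs are stated, and they exclude every post-baseline outcome.

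A reader might infer that the pattern model cannot be estimated with 182 patients. The documents do not support that: the covariate version can be fitted, and the baseline-only pattern lacks a slope at any sample size.

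**Conclusion.** The concern holds in this form. The baseline-propensity model cannot represent dropout that depends on unobserved z-scores; this follows from its definition and needs no assumption. Pattern main effects can be fitted but left the slope difference unchanged, with false 24-month differences of 0.152 to 0.216 passing through both checks. The sizes depend on assumed dropout mechanisms and, in A, on an assumed slope SD and intermittent rate. The reason for the lack of movement is structural. If averaging of pattern-specific slopes is meant, that average is not identified: about 9 of 91 patients per arm have no slope, and about 6 to 11 of 16 patterns lack a patient in at least one arm across 0 to 10% intermittent missingness.

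A reader might go further and infer that both checks would confirm the primary result whatever the dropout mechanism. That is not shown. Three mechanisms were tried, and only for the main-effects reading. Nor does the point reach pattern-mixture models as a class: collapsed and interacted with time and arm, they can address non-ignorable dropout, and the plan neither provides for this nor rules it out.

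The primary analysis itself is not at fault. What is missing is a check that can respond to the problem the plan names.

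**What to change.** Settle the following in the SAP before unblinding.

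1. Replace the baseline-propensity model with multiple imputation under explicit non-ignorable assumptions, either delta-adjusted or placebo-based, as a sensitivity analysis. Report the tipping point: the shift in LV T-D z units applied to the missing values at which the conclusion of the 1-df slope test changes.
2. If a pattern-mixture model is kept, collapse it to a few dropout groups, for example completers and dropouts, with group-by-time-by-arm terms and observed-proportion weights. State from which group the baseline-only patients borrow their slope.
3. Label that model as sensitivity only, and say why: it widens the standard error (0.141 to 0.194 in the two-group simulation) and can be biased when data are missing at random (−0.21 there). Finer groupings would be sparser, at about 9 patients per arm in each single dropout visit.
4. Correct the reference to a bivariate model.

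The cost is SAP wording and some programming. No new data are needed. The imputation analysis was not simulated here; its advantage is that the untestable assumption is stated and varied openly.

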9.3.2 Blood Biomarkers of Myocardial Remodeling

Natriuretic peptides (BNP), cardiac troponins (cTnT and cTnI), and Galectin-3 will be treated as continuous measures. We will apply the linear mixed effects model for between group comparisons of measures from the 5 time points. The unstructured mean model and linear in time model will be employed.

Aim 1.2.1: To establish the safety and tolerability of low-dose carvedilol.

9.3.3 Objective Safety Measures

Adverse events. The number of Grade 2-4 toxicities observed will be tabulated by treatment arm. Differences by treatment arm will be evaluated using Fisher exact tests.

Biomarkers. Liver function measurements (Bilirubin, AST, ALT) will be treated as continuous variables. Study participants will be considered to have elevated liver function if the measurements at 6, 12, 18, and 24 months are above the upper limit of the institutional reference range and higher than baseline pre-treatment level. These data will be coded such that those who are greater than 2-times the upper limit of the reference range will be considered to be clinically significant (Grade 1 if asymptomatic and requiring no intervention; Grade 2 if minimal/local/non-invasive intervention required). The frequency of individuals with elevated liver function measures will be compared between treatment groups using an exact test on 2x2 tables, stratified on CYP2D6. Logistic regression analysis will also be used to compare the frequency of elevated liver function between treatments, adjusted for covariates. Linear mixed-effects model for normally distributed data will also be used to compare the trends in liver function levels between the treatment groups. Procs MIXED and GLIMMIX will be used for longitudinal analysis of normally and non-normally distributed data, respectively. Proc GENMOD will also be used for normally and non-normally distributed data.

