8.0 CRITERIA FOR REMOVAL FROM PROTOCOL THERAPY AND OFF STUDY CRITERIA

8.1 Criteria for Removal from Protocol Therapy

- a) Physician determines it is in the patient's best interest.
- b) Inability to tolerate dose escalation from level 1 to level 2.
- c) Treatment interruption longer than 90 consecutive days.
- d) A cardiac event (see [Section 8.1.1](#) for definition).
- e) Pregnancy.
- f) Adverse Event requiring removal from protocol therapy (see [Section 13.4](#)).
- g) Diagnosis of a new malignancy requiring systemic chemotherapy or radiation.
- h) Adherence < 50% in any 90 day period.
- i) Emergency un-blinding (see [Section 5.0](#))
- j) Study is terminated by Sponsor.

Patients who are taken off protocol therapy do not require any additional study observations/evaluations unless they experienced a cardiac event or have become pregnant.

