Voluntary withdrawals: We assume that the proportion of patients in the placebo arm who will withdraw voluntarily by 24 months is 20% (10%/year); of note, this is less than the assumed overall attrition rate of 15%/year because attrition could occur due to other reasons such as toxicities, cancer recurrence, etc. With 125 patients in each arm at baseline, using Type I error=0.05, the study will have 80% power to detect a >15% absolute difference in the voluntary withdrawal rates between the two study arms.

WITH AMENDMENT #4:

Adverse events: We assume the rate of Grade 2-4 toxicities in the placebo group to be low, at 5%. At the end of the study, assuming 56 individuals remaining in each arm (19% attrition/year from the 91/arm at baseline), the study will have at least 80% power to detect an adverse event rate of 24.7% in the carvedilol group based on Fisher's exact test and Type I error=0.05.

Adherence to therapy: We will examine the difference in adherence rates by comparing the percent adherence by treatment group. With 91 study participants at baseline per arm, assuming a constant adherence rate of 90% in the placebo group, a between-measurement correlation of 0.6, 19% yearly attrition, and 2-sided alternative, there will be 80% power to detect an adherence rate of $\leq 70\%$ in the carvedilol group.

Voluntary withdrawals: We assume that the proportion of patients in the placebo arm who will withdraw voluntarily by 24 months is 26% (13%/year); of note, this is less than the assumed overall attrition rate of 19%/year because attrition could occur due to other reasons such as toxicities, cancer recurrence, etc. With 91 patients in each arm at baseline, using Type I error=0.05, the study will have 80% power to detect a >21% absolute difference in the voluntary withdrawal rates between the two study arms.

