13.3 Reporting of Adverse Events for Commercial Agents - via CTEP-AERS

Expedited AE reporting must use CTEP-AERS (Adverse Event Expedited Reporting System), accessed via <https://eapps-ctep.nci.nih.gov/ctepaers>

Commercial reporting requirements are provided in Table B. The commercial agent(s) used in this study are listed in the front of this protocol immediately following the Study Committee roster.

- COG requires the CTEP-AERS report to be submitted **within 7 calendar days** of learning of the event.
- Use the NCI protocol number and the protocol-specific patient ID provided during trial registration on all reports.

CTCAE term (AE description) and grade: The descriptions and grading scales found in the revised NCI Common Terminology Criteria for Adverse Events (CTCAE) version 5.0 will be utilized for AE reporting. All appropriate treatment areas should have access to a copy of the CTCAE version 5.0. A copy of the CTCAE version 5.0 can be downloaded from the CTEP website at:

http://ctep.cancer.gov/protocolDevelopment/electronic_applications/ctc.htm.

Table B

Reporting requirements for adverse events experienced by patients on study who have NOT received any doses of an investigational agent on this study.

CTEP-AERS Reporting Requirements for Adverse Events That Occur During Therapy with a Commercial Agent or Within 30 Days¹

Attribution	Grade 4		Grade 5
	Unexpected	Expected	
Unrelated or Unlikely			CTEP-AERS
Possible, Probable, Definite	CTEP-AERS		CTEP-AERS

¹This includes all deaths within 30 days of the last dose of treatment with a commercial agent, regardless of attribution. Any death that occurs more than 30 days after the last dose of treatment with a commercial agent that can be attributed (possibly, probably, or definitely) to the agent and is not due to cancer recurrence must be reported via CTEP-AERS.

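### Toxicity is compared on crude counts with no time at risk; if carvedilol patients stop drug more often, their later toxicities would be modestly under-counted

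*Combined protocol and SAP*

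**What the plan says.** The adverse-event analysis in section 9.3.3 is two sentences: "The number of Grade 2-4 toxicities observed will be tabulated by treatment arm" and "Differences by treatment arm will be evaluated using Fisher exact tests". It does not say whether events or patients are counted, who is in the denominator, or over what period.

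Four other sections decide how long a patient can contribute an event:

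- Section 8.1: "Patients who are taken off protocol therapy do not require any additional study observations/evaluations", with exceptions for a cardiac event or pregnancy.
- Section 4.3.2, under dose level 1: events within 30 days of stopping must be reported, and events of suspected, probable or definite relationship are reported with no time limit.
- Section 13.3: the expedited reporting table covers "Adverse Events That Occur During Therapy with a Commercial Agent or Within 30 Days". Its footnote adds later attributable deaths.
- Section 13.4: routine reporting covers Grade 2 or higher events probably or definitely attributed to study drug, plus anything reported through CTEP-AERS. Forms are submitted on Days 180, 365, 540 and 730.

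Three places bear on unequal stopping. Section 9.3.1 accepts that dropout may differ between arms and adds pattern-mixture and selection models, but for the echocardiographic analysis. Section 9.3.4 compares voluntary withdrawals by arm. Section 9.4 (Amendment #4) assumes 26% voluntary withdrawal on placebo by 24 months and states that "the study will have 80% power to detect a >21% absolute difference in the voluntary withdrawal rates between the two study arms".

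The power statement for adverse events in section 9.4 takes a 5% placebo rate, "assuming 56 individuals remaining in each arm (19% attrition/year from the 91/arm at baseline", and claims "80% power to detect an adverse event rate of 24.7% in the carvedilol group based on Fisher's exact test and Type I error=0.05".

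**The concern.** While a patient is on drug, toxicities are looked for at scheduled visits and calls. Once the patient is off drug, the plan schedules no contact at which a new event would be found. The active window is therefore the time on drug, and it is the same in both arms only if stopping is the same in both arms. A Fisher test on crude counts treats a patient who left at month 4 with no event exactly like one followed to month 24 with no event.

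If carvedilol is stopped more often, the crude comparison makes it look somewhat safer than it would under equal observation, and some power to show an excess is lost. Safety and tolerability of the two-year course is a stated secondary aim (section 1.2.1). The plan protects the echocardiographic outcomes against differential dropout and leaves the toxicity comparison without protection.

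**Working it through.** **1. The plan's own figures reproduce.** Attrition: 91 × (1 − 0.38) = 56.4, so 56 per arm. Exact two-sided Fisher power for 5% v 24.7% at 56 per arm, enumerating both binomials, is 0.800, as stated. For voluntary withdrawal, 26% + 21 points = 47%. Exact Fisher power for 26% v 47% at 91 per arm is 0.81, and the continuity-corrected sample size is 91 per arm. So 47% v 26% is a fair reading of the detectable alternative, although the plan does not write 47% and gives no direction.

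**2. Assumptions for the illustration (mine, not the plan's).** Toxicity and stopping have constant hazards, independent of each other. Events count until drug stops, or until 30 days later. Stopping by 24 months is 26% on placebo and 47% on carvedilol.

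Formulas, with time in years:

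- toxicity hazard h = −ln(1 − true 2-year risk)/2
- stopping hazard w = −ln(1 − proportion stopped)/2
- observed crude risk = h/(h + w) × [1 − exp(−2(h + w))]
- mean time on drug = (1 − exp(−2w))/w

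**3. Time on drug.** w = 0.151 (26%) and 0.317 (47%). Mean time is 0.26/0.151 = 1.73 years and 0.47/0.317 = 1.48 years, a ratio of 0.86.

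**4. Under-count at the plan's detectable rates.** h = 0.0256 for 5% and 0.142 for 24.7%.

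| Collection ends | Placebo, 26% stop | Carvedilol, 26% stop | Carvedilol, 47% stop | Ratio, 47% to 26% |
|---|---|---|---|---|
| at stop | 4.3% | 21.5% | 18.6% | 0.86 |
| stop + 30 days | 4.4% | 21.7% | 19.0% | 0.88 |

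The relative under-count is therefore 12-14%. With equal true risks of 5%, the arms would show 4.3% placebo v 3.7% carvedilol (4.4% v 3.8% with the 30-day window).

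**5. Early clustering.** Counting to the stop, if 50% of the toxicity hazard falls in the first three months, the ratio is 20.9/22.7 = 0.92. If 80% does, it is 22.7/23.7 = 0.96. The under-count shrinks to about 8% and 4%.

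**6. Power of Fisher's test, 91 per arm, true 5% v 24.7%.** Counting to the stop, power is 0.93 if both arms stop at 26% and 0.83 at 26% v 47%. With the 30-day window, the unequal case gives 0.85.

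**7. A harsher case.** Add the other attrition implied by section 9.4 (38 − 26 = 12 points) to both arms, giving 38% v 59%. With the 30-day window, equal true risks of 15% appear as 12.2% placebo v 10.4% carvedilol. Power for 5% v 24.7% is 0.79, rising to 0.94 if 80% of the hazard is early.

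**The case against.** The strongest case against the point has five parts.

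- **Collection does not end with the drug.** A reader might infer from section 8.1 that it does. Section 4.3.2 says otherwise: there is a 30-day window and open-ended reporting of related events, and related events are most of what section 13.4 collects. This stands. What remains is that off-drug capture is passive, and that section 4.3.2 sits under dose level 1 and fits poorly with section 8.1.
- **No excess stopping is forecast.** A reader might infer that the plan expects 47% to withdraw on carvedilol. It does not. The 21 points is an undirected detectable difference, and the adverse-event power calculation uses equal attrition. This stands, so the concern is conditional.
- **Toxicities that cause stopping are recorded.** They occur at or before the stop, so only later events after other stops can be lost. This stands. The independence model in the working, which lets every stop cut time at risk, therefore overstates the loss where stopping is itself due to a recorded toxicity.
- **Censoring at stop is not an unbiased cure.** If patients stop because they tolerate the drug poorly, censoring is informative. For drug-attributed events, the crude proportion describes harm actually experienced, while a Kaplan-Meier risk describes a setting in which everyone continues. This stands as a reason to report both and not to force a new primary test.
- **Other analyses look at tolerability.** Section 9.3.4 compares withdrawals, adherence and symptoms by arm, and section 11.6 records whether a voluntary withdrawal was due to side effects. These help interpretation but do not adjust the toxicity comparison.

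**Conclusion.** The point holds in a conditional and modest form. The toxicity comparison in section 9.3.3 ignores time at risk, active observation ends with protocol therapy, and the plan itself allows that dropout may differ by arm. If carvedilol patients stop more often, their later toxicities will be under-counted relative to placebo. At 47% v 26% stopping the relative under-count is about 12-14% under constant hazards independent of stopping, and about 4-8% if half to four-fifths of the hazard falls in the first three months. The hazard shape and the independence are assumptions.

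A reader might infer that the planned Fisher test is invalid or badly underpowered. The figures do not support that. Power at 91 per arm stays near or above the stated 80% in every case above, the lowest being 0.79 in the harsher case with the 30-day window. The unequal window also does not manufacture a carvedilol excess; it works the other way. The gap is one of completeness in a secondary safety aim, and it is cheap to close.

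**What to change.** In section 9.3.3:

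1. Define the endpoint as patients with at least one Grade 2 or higher toxicity, with all who started study drug as the denominator.
2. Keep the Fisher table. Beside it, report patient-years at risk and exposure-adjusted rates by arm.
3. Add time from first dose to first Grade 2 or higher toxicity, censored at the end of adverse-event collection, with a log-rank test and 24-month cumulative risk by arm.
4. State that this assumes stopping is unrelated to the risk of later toxicity, and show the results again with stopping treated as a competing event.

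Reconcile sections 4.3.2 and 8.1 on adverse-event collection after drug stops, so that the censoring date is defined for every patient whatever the dose level at stopping.

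The cost is analysis-plan wording and a standard supplementary analysis, with no new visits. It needs onset, dosing and last-contact dates. The adverse-event form is not in the documents, so it should be confirmed that onset dates are collected. The remaining weakness is the assumption of non-informative stopping, which the competing-event display makes visible but does not remove.

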1.2 Secondary Aims

1.2.1 To establish safety and tolerability of this two-year course of low-dose carvedilol, assessing both objective measures (hepatic function) and patient reported outcomes.

1.2.2 To examine the modifying effect of demographic, clinical, and molecular characteristics on the risk: benefit ratio from this two-year carvedilol intervention.

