12.0 EVALUATION CRITERIA**12.1 Common Terminology Criteria for Adverse Events (CTCAE)**

This study will utilize version 5.0 of the CTCAE of the National Cancer Institute (NCI) for toxicity and performance reporting. A copy of the CTCAE version 5.0 can be downloaded from the CTEP website

http://ctep.cancer.gov/protocolDevelopment/electronic_applications/ctc.htm.

Additionally, toxicities are to be reported on the appropriate case report forms.

Please note: 'CTCAE v5.0' is understood to represent the most current version of CTCAE v5.0 as referenced on the CTEP website (i.e., v5.02 and all subsequent iterations prior to version 6.0).

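### Read literally, the liver-safety case definition requires raised values at all four follow-up visits, so early leavers and patients with transient rises cannot be cases in the binary comparison

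*Combined protocol and SAP*

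**What the plan says.** Secondary aim 1.2.1 is safety and tolerability, "assessing both objective measures (hepatic function) and patient reported outcomes". Hepatic function is the only objective measure the aim names.

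Section 9.3.3 covers bilirubin, AST and ALT. Its case definition classes a participant as elevated "if the measurements at 6, 12, 18, and 24 months are above the upper limit of the institutional reference range", and adds that values must be "higher than baseline pre-treatment level". Its use is at patient level: "The frequency of individuals with elevated liver function measures will be compared between treatment groups using an exact test on 2x2 tables", stratified on CYP2D6, followed by a covariate-adjusted logistic regression. The same paragraph treats values "greater than 2-times the upper limit of the reference range will be considered to be clinically significant", coded "Grade 1 if asymptomatic and requiring no intervention" and Grade 2 if limited intervention is needed. It also plans mixed models of the trend in liver levels and a table of Grade 2-4 toxicities by arm.

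Three other sections bear on who has four values:
- The Amendment #4 part of 9.4 assumes 19% attrition per year, with drug intolerance among the causes, and 56 of 91 per arm remaining at the end.
- Section 8.1 requires no further study evaluations once a patient is off protocol therapy, except after a cardiac event or pregnancy.
- Section 13.4 takes patients with Grade 3 or higher toxicity, probably or definitely due to study drug, off therapy.

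**The concern.** A patient-level 2x2 table needs one rule that turns up to four visits and three analytes into yes or no. The only rule given lists the four visits with 'and'. Taken at its word, it counts sustained elevation through month 24 and nothing else. A patient with clearly raised values at 6 and 12 months who then stops, or whose values return to normal by 18 months, is not a case.

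The omission may not be random. If raised liver values lead to stopping, sections 13.4 and 8.1 together mean the later measurements will usually not exist. The rule would then leave out the patients a hepatic safety comparison most needs to count.

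Elsewhere the protocol does state a period rule when it has one in mind. Section 8.1 removes a patient for low adherence in any single 90-day period, and section 10.7 defines non-compliance over two consecutive periods. The liver sentence has no such wording.

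**Working it through.** **1. The plan's own figures.** No power is stated for the liver comparison. The nearest safety figure is in the Amendment #4 part of 9.4: 80% power for 5% against 24.7% adverse events, 56 per arm, Fisher's exact test, Type I error 0.05. Exact enumeration of the two-sided test gives 0.800, which reproduces it. The 56 also reproduces with attrition taken as a straight line: 91 × (1 − 2 × 0.19) = 56.4. Compounding gives 91 × 0.81² = 59.7, so the plan did not compound.

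**2. Patients who cannot meet the literal rule for lack of a 24-month value.**
- From 9.4: (91 − 56)/91 = 35/91 = 38.5% per arm.
- From 9.5.2 (114 of 182 complete all time points): 1 − 114/182 = 37.4%.
- If 19% per year compounded: 1 − 0.81² = 34.4%.

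This step needs no assumption about liver-elevation rates.

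**3. Illustrative case counts.** The documents give neither a per-visit elevation rate nor a between-visit correlation, so both are assumed. Let p be the chance that a patient meets the criteria at a given visit. The correlation is that of an underlying normal variable, equal between visits. Loss is 9.5% of the randomised number per six months, so 90.5%, 81%, 71.5% and 62% are seen at 6, 12, 18 and 24 months.

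Hand check with p = 0.10 and independent visits:
- All four: 0.62 × 0.10⁴ = 0.00006.
- Any observed visit: 0.095 × (0.100 + 0.190 + 0.271) + 0.62 × 0.344 = 0.267.

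The simulation (400,000 patients) gives 0.0001 and 0.267. Selected results, as a share of those randomised:

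| p per visit | Correlation | All four visits | Any visit | Cases of 91: all four / any |
|---|---|---|---|---|
| 0.05 | 0.3 | 0.03% | 12.8% | 0.03 / 11.6 |
| 0.10 | 0.3 | 0.17% | 23.3% | 0.15 / 21.2 |
| 0.10 | 0.6 | 0.92% | 19.2% | 0.84 / 17.5 |
| 0.20 | 0.6 | 2.9% | 34.0% | 2.6 / 30.9 |
| 0.20 | 0.9 | 7.1% | 25.4% | 6.5 / 23.1 |

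Over p from 5% to 20% and correlation from 0 to 0.9, the all-four rule yields 0 to 6.5 cases of 91 and the any-visit rule 6.6 to 42.5.

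**4. What this does to the test, as an example.** Suppose the per-visit rate were 10% on placebo and 20% on carvedilol, with correlation 0.3 to 0.7. Two-sided Fisher power at 91 per arm, unstratified, is about 52% to 65% with the any-visit rule and at most about 5% with the all-four rule.

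The model does not treat the three analytes or the above-baseline condition separately; both are folded into p.

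**The case against.** **Other readings of the sentence.** The list of months may simply name the scheduled post-baseline draws, each to be judged in turn. Strict conjunction, applied evenly, would also require bilirubin, AST and ALT all to be raised, which is unlikely to be meant. The paragraph says nothing about missing visits, so exclusion of early leavers follows from the literal rule and is not prescribed. All this stands, and any-visit may well have been intended. But the text does not say so, and a patient-level table needs one definition: in the p = 0.10, correlation 0.6 example, two analysts could report about 1 or about 17 cases per arm from the same data.

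**Other safeguards.** A reader might infer that a hepatic signal would be lost from the plan altogether. The documents do not support that. The mixed models of liver levels use transient rises and partial follow-up. The Grade 2-4 table, the documentation of adverse events leading to withdrawal (8.1.1) and committee review of repeated related Grade 3-4 toxicity (9.5.1) do not depend on the rule. The adverse event route is only a partial backstop: 9.3.3 codes asymptomatic values above twice the limit as Grade 1, and 13.4 collects Grade 2 or higher only if probably or definitely related, apart from expedited reports. A comparison of mean trends also does not replace a count of patients with abnormal values.

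**Grading.** A reader might also see a conflict between the Grade 1 and 2 coding in 9.3.3 and section 12.1 ("This study will utilize version 5.0 of the CTCAE"). That cannot be shown from these documents: 12.1 concerns toxicity and performance reporting, 9.3.3 describes coding of laboratory data for analysis, and the CTCAE text is not supplied.

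**Persistent elevation is a legitimate endpoint.** True, and it can be kept as a separate category.

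**Conclusion.** The point holds for the binary liver comparison and the logistic regression built on it. Under the literal wording, about 38% of each arm (35 of 91; 34% if attrition compounds) could not be cases because they have no 24-month value, and completers with any normal visit are excluded as well. That share rests only on the plan's attrition assumption. The likely result is few events and possible omission of patients who left because of liver toxicity.

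How few is not known. The counts rest on assumed elevation rates and correlations, and the upper end of the range (6.5 of 91) is not negligible. The mixed models, the Grade 2-4 table and the primary endpoint are unaffected.

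**What to change.** In 9.3.3, replace the case definition with one that states:
- a case is a patient with bilirubin, AST or ALT above the institutional upper limit and above that patient's baseline at one or more of the scheduled 6-, 12-, 18- or 24-month visits;
- the denominator is patients with at least one post-baseline liver value, and those who leave early are classified on the values available;
- persistent elevation is reported as a separate category, with its visit requirement spelled out.

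Limit the definition to scheduled visits, because the documents do not show that unscheduled values are collected systematically. Do not use all treated patients as the denominator, since that would count patients with no post-baseline value as non-cases.

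The cost is a short SAP edit; the scheduled measurements are already in the study calendar (7.1). The small downside is that isolated fluctuations will also be counted, which the separate persistent category helps the reader to judge.
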